### 10.14/ 90-day follow-up

- Record site ID code, 3-digit study ID, and the unique 3 letter identifier in the indicated fields at the top of each page.
- If telephone contact was not made and the information was not otherwise collected, check the indicated box on line 1
- Fill out a row for each telephone contact attempted.
- Enter the date and time of the attempted contact in column 1 and 2.
- Indicate whether contact with patient or LAR occurred by checking the appropriate “Yes/No” box in column 4.
- If “No,” indicate the action taken by checking the appropriate box in column 5.
- If contact was made, indicate if it was directly with the study patient by checking the appropriate “Yes/No” box on line 3.
- If “No,” record the name of the contact person on line 3, their relationship with the study patient on line 4, and indicate if he contact person was the LAR by checking the appropriate “Yes/No” box on line 5.
- Answer question s about the patient’s current level of functioning on lines 6-9 by checking the appropriate “Yes/No” box.
- Indicate the type of location in which the study patient currently resides by checking the appropriate box on line 10.
- Add any comments about the patient’s level of function or alternative sources of information in the comment section.
- Record the name of individual completing the 90-day follow-up CRF and the date completed on line 11.

## 11./ Study Associated Risks and Risk Mitigation

a./ Although not expected to occur with modest TH to 34°-35°C, patients can develop:

b./ (1) persistent severe bradycardia (heart rate <30 associated with mean arterial pressure <65 without vasopressors); (2) uncontrolled bleeding and (3) intractable ventricular arrhythmias, there. In the event any of these conditions happens, TH protocol will be early terminated following clinical guidelines.

(4)There is a slightly Increased risk of infection, study subjects are closely monitored for infection and the appropriate use of antibiotics should be initiated as standard of care; (5) there is a mild risk of changes in fluid and chemical balance, this patient population is closely monitored and correction is implemented as standard of care; (5) there is a mild to moderate risk of hyperglycemia occur, this patient population is closely monitored and correction should be implemented as standard of care; (6) there is a slight reduction in the ability of blood clotting mechanism, this patient population is closely monitored and corrections should be implemented as standard of care.

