### 1.2/ Study Aims and Objectives

We will conduct the CHILL-pilot single-center RCT of TH in patients with COVID-19 and ARDS with P/F < 250 to address the following specific aims:

1. **Aim 1: Analyze the safety and feasibility and the potential lung protective effect of treating patients with COVID-19 infection and ARDS with P/F < 200 with mild TH (core temperature 34°-35°C) + NMB for 48h compared with controls receiving standard temperature management.** We expect the TH-treated group to achieve targeted temperature within 4h of randomization and to maintain TH for 48h without significant increase in serious adverse effects compared with the control arm.
2. **Analyze the potential lung protective effect of mild TH (core temperature 34°-35°C for 48h) and NMB in patients with ARDS and P/F < 200 compared with controls receiving standard temperature management.** We expect the TH-treated group to trend toward having more 28-day VFDs (primary) and 28-day ICU-FDs, and improved day-3 driving pressure and OSI than the controls.
3. **Evaluate the effects of TH on systemic inflammation and extrapulmonary organ dysfunction.** We expect the treated group to have reduced levels of proinflammatory mediators and lower Sequential Organ Failure (SOFA) scores than controls.

The proposed pilot study will determine whether we can safely include patients with COVID-19 and ARDS in our larger Phase IIb trial of TH and NMB in patients with ARDS. It will help us determine whether the 48h duration of cooling is sufficient.

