### 7.3/ 5.3 Blood Laboratory values data collection

Hematology (WBC, Hgb, Hct, Platelets), Chemistry (Potassium, Bicarbonate, BUN, Creatinine, Glucose, Magnesium, Phosphate, Albumin, Bilirubin AST/ALT results measured by standard of care and recorded as per study data collection requirements.

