## 8/ Study Interventions

### Temperature management:

1. Therapeutic Hypothermia Arm: The participating ICUs share an established institutional protocol for NMB and TH, which will facilitate rapid mobilization of treatment following randomization. Sedation will be adjusted to achieve a RASS -4 score and cisatracurium (Nimbex™) will be initiated and adjusted to the lowest rate that achieves nerve stimulation response of 2 twitches in train-of-four monitoring, reduction in ventilator dyssynchrony to acceptable levels, and elimination of shivering. NMB will be continued through the rewarming phase at least until core temperature reaches 35.5°C (~54h total time). Note that if the supply of Nimbex in the Clinical Pharmacy is insufficient to treat the subject, a supply of study-only Nimbex is available in the Investigational Drug Service Pharmacy.

Since the objective of CHILL-pilot is to test the effectiveness of cooling to a target temperature rather than the performance of a specific cooling device, patients in the TH arm will be cooled using one of the institution's two FDA-approved surface cooling devices, Blanketrol II cooling blankets or Arctic Sun™ cooling system. Core temperature will be reduced to 34°-35°C as quickly as possible and TH maintained for 48h. Patients will then be rewarmed to 36°C by 0.3°C/h and the cooling device removed. Post-cooling fever suppression is not part of the CHILL-pilot protocol. Cooling parameters were selected to optimize risk:benefit ratio. The criteria for early termination of hypothermia are persistent severe bradycardia (heart rate < 30 associated with mean arterial pressure <65 without vasopressor agents), uncontrolled bleeding, and intractable ventricular arrhythmias.

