**Patient:**

Home Phone: -- Cell: --

Email: \_\_\_\_\_

**Legally Authorized Representative (Name):** \_\_\_\_\_

Home Phone: -- Cell: --

Email: \_\_\_\_\_

**Additional Contact 1:** Name: \_\_\_\_\_ Relationship to patient: \_\_\_\_\_

Home Phone: -- Cell: --

Email: \_\_\_\_\_

**Additional Contact 2:** Name: \_\_\_\_\_ Relationship to patient: \_\_\_\_\_

Home Phone: -- Cell: --

Email: \_\_\_\_\_

**Additional Contact 3:** Name: \_\_\_\_\_ Relationship to patient: \_\_\_\_\_

Home Phone: -- Cell: --

Email: \_\_\_\_\_

**Additional Contact 4:** Name: \_\_\_\_\_ Relationship to patient: \_\_\_\_\_

Home Phone: -- Cell: --

Email: \_\_\_\_\_

**Additional Contact 5:** Name: \_\_\_\_\_ Relationship to patient: \_\_\_\_\_

Home Phone: -- Cell: --

Email: \_\_\_\_\_

**Additional Contact 6:** Name: \_\_\_\_\_ Relationship to patient: \_\_\_\_\_

Home Phone: -- Cell: --

Email: \_\_\_\_\_

SITE ID		PATIENT ID				LETTER CODE			

## DAILY DATA – Day 01

(To be completed as close to 0800 as possible on the day after randomization)

Form Completed by \_\_\_\_\_            
MONTH D D Y Y Y Y TIME (0-

Vital status  Alive  Dead (If alive, skip to line 5)

Time of death:            
MONTH D D Y Y Y Y TIME (0-2400)

Cause of death (from discharge summary/discussion with ICU team), then skip to question 11.

- Respiratory failure  Cardiac (arrhythmia, ACS, cardiogenic shock)  Multi-organ failure  
 Refractory shock  Intraabdominal (perforation, compartment)  Withdrawal of care  
 Neurological devastation  Severe sepsis  Refractory acidosis  Hemorrhage

Is patient still receiving NMB?  Yes  No If "Yes" skip to question 9

Date/Time NMB discontinued:            
MONTH D D Y Y Y Y TIME (0-2400)

Reason for discontinuation:  Refractory bradycardia  Possible drug reaction  
 Decision of ICU provider  Decision of family

Date/Time: neuromuscular function (4 twitches/TOF) returned:            
or  Did not return MONTH D D Y Y Y Y TIME (0-2400)

Is patient in hypothermia group?  Yes  No If "No" skip to question 14

Minutes to reach 35°C from randomization:    from initiation of cooling:

Still being cooled?  Yes  No If "Yes" skip to question 15

If No, when was cooling stopped?            
MONTH D D Y Y Y Y TIME (0-2400)

Reason for discontinuation:  Refractory bradycardia with hypotension  Hemorrhage  

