 Intractable ventricular arrhythmia  Decision of ICU provider  Decision of family

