### Skip to question 15.

If in the Control arm, received therapeutic hypothermia in last 24 hrs?  Yes  No  N/A

Still intubated or receiving Assisted Breathing?  Yes  No  N/A

If "No," when was patient extubated or UAB for ≥48 hours?            
MONTH D D Y Y Y Y TIME (0-2400)

Was RRT started since randomization?  Yes  No  N/A

If RRT had been previously initiated has it stopped since randomization?  Yes  No  N/A

Since randomization did the patient have any of the following:

Bradycardia (with mean arterial pressure < 65 mm Hg or needing pressors)  Yes  No

Significant Bleeding (Required IR, Surgery or >3u pRBCs)  Yes  No

Diagnosis of new pneumonia  Yes  No

**Vital signs (Record highest and lowest values since randomization; If only one value, record as lowest and check the "Single" box.**

Systolic BP: Lowest:    Highest:    mm Hg Single

Diastolic BP: Lowest:    Highest:    mm Hg Single

CVP: Lowest:   Highest:   cm H2O CVP not available  Single

Mean arterial pressure: Lowest:    Highest:    mm Hg Single

--	--	--	--	--	--	--	--	--	--

SITE ID PATIENT ID LETTER CODE

Record date / /  and time  of randomization  
MONTH D D Y Y Y Y TIME (0-2400)

Check box in first column of table below indicating randomization time.

Record date / /  and time  cooling started or check Not Cooled   
MONTH D D Y Y Y Y TIME (0-2400)

For each 2 hr block from randomization until 0800 of DAY AFTER randomization record highest and lowest temperature and lowest SpO2 and the FiO2 and Mean Airway Pressure measured closest to the SpO2 reading. If only one temperature measurement for block, enter in "Low" field and check box. If no SpO2 value for block, check "None" box.

Check box indicating randomization time	Time period	Temp (°C) If only one value record as "Low" and check box	Site of Temp measurement	Low SpO 2 (%) *	FiO 2 (%)	Mean airway pressure (cm H 2 O)
Day of Randomization						
	0001 to 0200	High: _____ Low: _____ 	 Esophageal  Urinary  Peripheral  IV	None 		

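### Ventricular arrhythmia, a named harm that ends cooling, is prompted for only in the hypothermia arm; the daily checklist asked in both arms leaves it out

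*Protocol*

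**What the plan says.** Section 8 (temperature management) sets three criteria for ending hypothermia early: severe bradycardia with low arterial pressure, "uncontrolled bleeding, and intractable ventricular arrhythmias". Section 11 lists the same three as risks: "uncontrolled bleeding and (3) intractable ventricular arrhythmias", preceded by bradycardia.

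The daily case report forms carry a short event checklist that applies to both arms. On the Day 1 form (line 18) it opens "Since randomization did the patient have any of the following" and offers three items: bradycardia with low pressure or need for pressors, significant bleeding, and new pneumonia. The same three items appear on the Day 3 and Day 4 forms (line 17) and the Day 7 form (line 13).

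"Intractable ventricular arrhythmia" appears elsewhere, as one option under the reason cooling was discontinued (Day 1 line 13; line 12 on the Day 3 and Day 4 forms). That item sits behind a filter, "Is patient in hypothermia group", and a No answer sends the patient past it.

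Aim 1 (section 1.2) expects the cooled group to hold its temperature "without significant increase in serious adverse effects compared with the control arm". The SAP plans a chi-square test on SAEs.

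**The concern.** A between-arm safety comparison needs each harm to be looked for in the same way in both arms. For ventricular arrhythmia the forms ask a specific question of one arm only, and of that arm only when cooling has stopped. In every other patient someone must notice the event, judge it reportable and write it as free text on the adverse event form. Blinding is not possible (section 1.1), so staff know who is cooled and know that arrhythmia is a listed risk of cooling. Section 2.2.1.1.1 also limits non-serious reportable events to those that differ from the expected course of ARDS, which leaves room to regard an arrhythmia in a control patient as part of the illness.

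The pilot is meant to inform whether COVID-19 patients can safely enter the Phase IIb trial. With about 10 patients per arm, one or two events captured differently would change how the safety table reads.

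**Working it through.** The plan states no figure on this point, so there is nothing to reproduce. The main check is to set the three named conditions against the form items.

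| Condition that ends cooling (sections 8 and 11) | Cooling-stop reason (hypothermia arm only) | Daily checklist item (both arms) |
|---|---|---|
| Severe bradycardia with low pressure | Yes | Yes |
| Uncontrolled bleeding | Yes, as hemorrhage | Yes, as significant bleeding |
| Intractable ventricular arrhythmia | Yes | **No** |

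The routing confirms that the middle column excludes controls. On Day 1 a No at line 9 leads to line 14, past line 13. On Days 3 and 4 a No at line 9 leads to line 13, past line 12. The Day 7 form has no stop-reason item and the same three-item checklist. The Day 2 form is not in the text available, but section 10.5 gives one set of instructions for Days 2 and 3.

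Possible size, for illustration only. The rates below are assumptions, since the documents give none. Let p be the true rate in both arms and s the share of control events that reach the adverse event form, with full capture in the hypothermia arm. The false excess is p × (1 − s).

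- p = 10%, s = 90%: 0.10 × 0.10 = 1 percentage point
- p = 10%, s = 50%: 0.10 × 0.50 = 5 points
- Across p = 5-20% and s = 50-90%: from 0.05 × 0.10 = 0.5 points to 0.20 × 0.50 = 10 points

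At p = 10% and 10 per arm, the chance of at least one recorded event is 1 − 0.90^10 = 65% under hypothermia. In controls it is 1 − 0.95^10 = 40% (s = 50%) to 1 − 0.91^10 = 61% (s = 90%). Full capture in the hypothermia arm is generous, because an arrhythmia that did not end cooling is not prompted for there either.

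Precision even with perfect capture (20 patients, 1:1, so about 10 per arm):

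- 0/10 events leaves a one-sided 95% upper bound of 1 − 0.05^(1/10) = 25.9%.
- 4/10 v 0/10: uncorrected chi-square = 20 × (4 × 10)² / (10 × 10 × 4 × 16) = 5.0, p = 0.025; Fisher exact p = 2 × 210/4845 = 0.087.
- 5/10 v 0/10: Fisher exact p = 2 × 252/15504 = 0.033.

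**The case against.** The strongest reply is that the event is not lost in controls, and most of that reply stands. Section 2.2.3.2 has site staff record all adverse events, in either arm. The adverse event form begins by asking whether there were any. The schedule of events marks adverse event monitoring in every column from day 0 to day 90. An intractable ventricular arrhythmia would ordinarily count as life-threatening, and such events in the first three study days are SAEs in either arm. Arrhythmia is also part of a cause-of-death option in both arms. A reader might infer that the event can be recorded only as a reason for stopping cooling; these provisions show otherwise.

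A reader might also infer that the design makes hypothermia look worse. The documents do not support that. The stop-reason item describes adherence, and the SAP tests SAEs and does not compare stop reasons between arms. A count taken from the stop-reason box alone, set against none in controls, is not an analysis anyone has planned.

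What the reply does not remove is the difference in prompting. A general question followed by free text is weaker than a named Yes/No item, the cause-of-death option covers fatal events only and merges arrhythmia with other cardiac causes, and the plan already chose named items for the other two stop conditions.

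A further tempting reading concerns clotting. Section 11 says "there is a slight reduction in the ability of blood clotting mechanism, this patient population is closely monitored", while the laboratory list in section 7.3 ("Hematology (WBC, Hgb, Hct, Platelets), Chemistry (Potassium, Bicarbonate, BUN, Creatinine, Glucose, Magnesium, Phosphate, Albumin, Bilirubin", then liver enzymes) has no coagulation test. This is not an imbalance between arms. No clotting test is listed for either, and platelets and significant bleeding are recorded equally in both. Whether the hospital's hypothermia order set includes clotting tests cannot be told, because section 8 gives only the modifications to it. Abstracting PT/INR or aPTT when available would depend on what unblinded clinicians chose to order, so it could introduce the same kind of unequal ascertainment.

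**Conclusion.** The point holds in a limited form. Of the three conditions that end cooling, two are asked about by name in both arms. The third, ventricular arrhythmia, is asked about by name only in cooled patients whose cooling stopped; for everyone else it relies on general AE and SAE reporting by unblinded staff. Ascertainment is therefore unequal by arm.

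The size of any bias cannot be determined from the documents, and neither can its direction in the planned SAE comparison. The 0.5 to 10 point range rests wholly on the assumed event rates and capture shares. Section 11 itself does not expect these events at the target temperature, so there may be none. With about 10 per arm, neither equal nor unequal capture would support a precise comparison. This is a low-cost improvement to the forms and does not invalidate the safety outcome. The clotting question does not form part of it.

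**What to change.** Add a Yes/No item for ventricular arrhythmia, worded to match the risk as sections 8 and 11 name it, to the existing both-arm event checklist on the Day 1, 2, 3, 4 and 7 forms. Keep it separate from the cooling-stop reason, which can stay as it is for adherence. In the safety tables, report it by arm next to bradycardia, significant bleeding and new pneumonia.

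The cost is one tick-box per form and a matching line in the section 10 instructions. Unblinded staff would still complete it, and about 10 patients per arm would still give little precision. What changes is that the same question is put to every patient. No clotting tests need to be added.

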## 12./ Adverse Event Reporting

Adverse events will be classified by according to the following definitions (21 CFR 312.32):

### 1. *What is not an Adverse Event*

Organ failures or death related to ARDS or the patient's underlying condition that are systematically captured by the protocol (primary or secondary outcomes) should not be reported as AEs unless they are considered study-related.

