
We have been approved for funding by Department of Defense (DoD) to support for a 4-year multicenter RCT of TH+NMB for 48h vs. standard of care with contract to be completed June 1, 2020 and with enrollment to begin in Fall of 2020. This study was designed prior to the onset of COVID-19, which is now the most common cause of ARDS and will likely continue to be in the Fall, 2020 and perhaps beyond. Therefore, it is important to decide whether patients with COVID-19 ARDS should be enrolled in our CHILL trial. Therefore, we will conduct a 20-patient pilot safety and feasibility trial of our CHILL TH+NMB treatment vs. control in COVID-19 patients with ARDS who meet the inclusion/exclusion criteria of our DoD-funded trial. The major objective of the proposed pilot trial is to determine whether it is safe and feasible to include patients with COVID-19 ARDS in our Phase IIb CHILL RCT of TH+NMB vs. control in patients with moderate to severe ARDS.

The pilot will be conducted at the University of Maryland Medical Center. To facilitate randomization within the inclusion window, we will consent and enroll based on partial fulfillment of randomization criteria and randomize once all criteria are met. Patients will be

eligible for enrollment when they have been diagnosed with COVID-19 by PCR, and have met all Berlin criteria for moderate to severe ARDS within the 48h inclusion window except the P/F ratio  $\leq 200$  but will not be randomized until P/F ratio (measured or imputed based on SpO2) is  $\leq 200$  (while on  $\geq 8$  cm H2O PEEP and  $\geq 0.6$  FiO2). We plan to randomize a total 20 patients over 4 months to hypothermia (core temperature 34°-35°C for 48h) plus NMB or usual temperature management. The primary outcome measures will be effectiveness of cooling in achieving and maintaining the target temperature and safety measures. Secondary outcomes will include 28-day ventilator-free days (VFDs), 28-day ICU-free days, oxygen saturation index (OSI), driving pressure, Sequential Organ Failure Assessment (SOFA) score, 60-day and 90-day survival, 90-day functional assessment, cognitive assessment at ICU and hospital discharge, and biomarkers of inflammation and lung injury. Since the nature of the intervention precludes blinding, all treatment and clinical decision making related to study outcomes will be protocolized and compliance with study protocols will be monitored.

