##### 2.2.1.1.1 Responsibilities of the CEC:

1. The CEC will meet bi-weekly to monitor progress with enrollment, randomization, retention, and data quality milestones and re-evaluate and revise as needed all study protocols.
2. The CEC will review suggestions for protocol amendments from all CHILL-pilot personnel and make final decisions about modifying protocols.
3. [name] will prepare reports for DSM meetings with input from [name].
4. Serious/Reportable Adverse Event (SAE/RAE) Adjudication and Reporting: The following is an initial plan for adverse event (AE) reporting (the plan will be revised by the CHILL leadership with input from CHILL personnel and the CHILL Data Safety monitor, [name], based on experience with the ongoing study). Serious Adverse Events are defined as any deaths, life-threatening events, or events that prolong hospitalization that occur within the first three study days (which includes the period of cooling and rewarming in the Therapeutic Hypothermia arm). All SAEs will be reviewed by [name] based on information provided by [name]. [name] will report the SAE, including his assessment of relatedness to study procedures, to the UMB IRB and the Data and Safety Monitor, [name] within 48 hours of discovery. Reportable AEs (RAEs) that do not meet the threshold for SAEs are defined as any clinically important untoward medical occurrence in the first study week which is different from what is expected in the clinical course of a patient with ARDS. All other AEs will be tabulated without case-by-case review unless a difference between treatment groups calls for review of a group of cases. [name] will submit monthly tabular reports of all SAEs/RAEs to [name] and will submit tabular summaries of all AEs to [name] every 6 months. The AE summary will be included in the bi-annual review by [name].
5. Ongoing Scientific Review: CEC members and any other interested CHILL-pilot personnel may bring new information with potential impact on study protocols and analysis to the attention of the entire CEC. The topic will be added to the CEC meeting agenda and background information distributed with enough lead time to allow a productive discussion.
6. Processing Requests for Sample Sharing: [name] will provide to the CEC all information about sample sharing requests and information about sample availability

and status of the CHILL-pilot biomarker analysis to inform decisions by the CEC about the priority of sample sharing requests.

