#### 2.3.1.2 MPI for CC

[name] is Leader of the Clinical Operations Group. Responsibilities include:

1. [name] will interact with the CHILL-pilot study coordinator, [name], to:
  - a. oversee efficient operation of the Participating ICUs, and to
  - b. ensure that all members of the Chill-pilot Clinical Team (e.g. Pulmonary and Critical Care fellows; cross-covering coordinators) are appropriately trained in CHILL-pilot study protocols.
2. Will adjudicate AEs and SAEs with [name] and assist in preparing reports for the DSMB

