### 3.5/ Retention Strategies

We anticipate that most participating subjects will remain hospitalized, likely in the ICU, through study day 7 and accessible to study personnel. Patients will be seen daily by study personnel through the first 7 days for data collection, protocol adherence, and collection of research samples. Beyond study day 7 patient status will be monitored by examining the medical record and, as needed, bedside visit. Study personnel will complete CRFs for ICU discharge, study day 28 status, and hospital discharge. The hospital discharge CRF will contain patient disposition and contact numbers, including the patient's LAR to facilitate 60-day and 90-day follow-up.

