#### 10.12/ Adverse Event CRF

Refer to Section 12: Adverse Event Reporting

- Record site ID code, 3-digit study ID, and the unique 3 letter identifier in the indicated fields at the top of each page.
- Indicate on line 1 whether the patient had any adverse event (AE) by checking the appropriate “Yes/No” box.
- If “Yes,” fill out one column for each adverse event.

- In row 2 give a brief description of the AE.
- In row 3, record the name of the individual entering data about the AE.
- Record the date and time the AE was first detected in rows 4 and 5, respectively. If unknown, check the “?” box.
- Record the date and time the AE was resolved in rows 6 and 7, respectively. If unknown or if not resolved check the “?” box.
- Indicate the most appropriate severity grade of the AE by checking the appropriate box in row 8 (check only one box).
- Indicate whether the AE was serious by checking the appropriate “Yes/No” box in row 9.
- Indicate whether the AE was expected by checking the appropriate “Yes/No” box in row 10.
- Indicate likelihood of relatedness to the study intervention by checking the appropriate box in row 11 (check only one box).
- Indicate the action taking with the study intervention by checking the appropriate box in row 12 (check all that apply).
- Indicate other actions taken by checking the appropriate box in row 13 (check all that apply).
- Record the outcome by checking the most appropriate box in row 14 (check only one box).
- Enter the name of the investigator who made the assessment about severity and study relatedness in row 15.
- Enter the date of the assessment in row 16.

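### The SAP compares SAEs between arms without saying which of the protocol's conflicting SAE wordings applies, and Section 12 filters ARDS deaths and organ failures by unblinded attribution

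*Protocol*

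**What the plan says.** Protocol Section 1.1 sets the primary outcome: "The primary outcome measures will be effectiveness of cooling in achieving and maintaining the target temperature and safety measures". The SAP gives the between-arm SAE analysis one sentence, naming a chi-square test. It does not define an SAE, give a time window, say whether patients or events are counted, or point to a protocol section.

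The protocol words the matter in several ways:

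- **Section 2.2.1.1.1, item 4**, which calls itself an initial plan: "Serious Adverse Events are defined as any deaths, life-threatening events, or events that prolong hospitalization that occur within the first three study days". Cause and relatedness play no part.
- **Section 2.2.3.2, item 2** sends early deaths and life-threatening events for review, and adds unexpected SAEs in the first study week, which does not fit a three-day definition.
- **Section 12, subsection 1** removes deaths and organ failures due to ARDS or the underlying condition "that are systematically captured by the protocol (primary or secondary outcomes"). These "should not be reported as AEs unless they are considered study-related".
- **Section 12, subsection 3** treats seriousness as a grade given to an AE. Its list is wider than that of Section 2.2.1.1.1 and it has no three-day limit.
- **Section 12, Reporting requirements** sends deaths and life-threatening events with a temporal link to study procedures for review, together with unexpected SAEs.

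The instruction for the AE form (Section 10.12) reads "Refer to Section 12: Adverse Event Reporting".

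**The concern.** The pilot is meant to show whether COVID-19 ARDS patients can safely enter the larger trial. Two analysts working from the same patients, one using Section 2.2.1.1.1 and one using the Section 12 AE form, could produce different SAE tables, and both could say that they had followed the protocol.

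The Section 12 route also filters the count by attribution. Whether an ARDS death or organ failure counts depends on whether someone links it to a study procedure, and that person knows the arm: "Since the nature of the intervention precludes blinding" (Section 1.1). The count can then differ between arms because the judgement differs, not because the events do. It could make hypothermia look worse, if deaths after cooling are more readily called related. It could make it look better, if real excess deaths are put down to ARDS in both arms.

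**Working it through.** **1. One patient under each wording.** Take a death from ARDS on study day 2, judged unrelated to study procedures.

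- Section 2.2.1.1.1: a death within three study days, so an SAE.
- Section 12, subsection 1: survival is a secondary outcome (Section 1.1), so the exclusion applies and the death is not an AE. Subsection 3 grades only AEs, so it is not an SAE.
- Section 12, Reporting requirements: the death goes for review if it is temporally linked to a study procedure, which needs no causal judgement.

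Subsections 1 and 3 of Section 12 work in sequence and agree with each other. The contradiction is with Section 2.2.1.1.1, and the two review rules fit neither cleanly.

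**2. Where the arm enters.** Section 2.2.1.1.1 treats the arms alike. Under Section 12, subsection 5, an event is related if it follows a study procedure in time and could have been produced by it. The assessors know the arm, and no blinded adjudication is described.

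**3. Size.** There is no figure in the plan to reproduce: the documents give no SAE or early-death rate, and the SAP states an alpha only for ventilator-free days. Assumptions: 10 patients per arm (20 patients, 1:1 within strata), the same number of early ARDS deaths in each arm, and no other SAE.

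For counts a and b, the uncorrected Pearson statistic is 20 × [a(10−b) − b(10−a)]² / [10 × 10 × (a+b) × (20−a−b)]. The Newcombe interval combines the Wilson limits of each arm: 0/10 has 0 to 0.2775, 1/10 has 0.0179 to 0.4042, and 3/10 has 0.1078 to 0.6032.

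One death per arm:

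- Section 2.2.1.1.1: 1 v 1, difference 0.
- Section 12, none judged related: 0 v 0.
- Section 12, only the hypothermia-arm death judged related: 1 v 0, difference 0.10. Statistic 20 × 10² / (100 × 1 × 19) = 1.05, Pearson p = 0.305, Fisher p = 1.0. Lower limit 0.10 − √[(0.10 − 0.0179)² + 0.2775²] = −0.19; upper limit 0.40.

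Three deaths per arm:

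- Section 2.2.1.1.1: 3 v 3, difference 0, 95% CI −36 to +36 points.
- Section 12, none judged related: 0 v 0, 95% CI −28 to +28 points.
- Section 12, only the hypothermia-arm deaths judged related: 3 v 0, difference 0.30. Statistic 20 × 30² / (100 × 3 × 17) = 3.53, Pearson p = 0.060, Fisher p = 0.21. Lower limit 0.30 − √[(0.30 − 0.1078)² + 0.2775²] = −0.04; upper limit 0.60.

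Three per arm is extreme for this trial: exclusion 10 in Section 3.2.2 removes patients not expected to survive 72 h.

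**4. Prompted events, a minor matter.** The Day 4 form closes at 0800 on day 4 and the Day 7 form at 0800 on day 7, which is 72 h. Day 7 line 13 and its instruction in Section 10.7 ask about bradycardia, bleeding and new pneumonia over 24 h, so 72 − 24 = 48 h are not prompted. The gap is the same in both arms, and the open AE form still covers it.

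**The case against.** The other side has several good points.

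- Leaving expected outcomes out of AE reporting limits the reporting burden in an ICU trial. That reason stands for reporting. It does not make the filtered count a sound basis for comparing arms.
- Section 2.2.1.1.1 might be an expedited-reporting rule, with Section 12 the real definition. But it is worded as a definition, and no text says which one feeds the chi-square. If it is set aside, the attribution-filtered count is what remains.
- There are safeguards. The investigator leading clinical operations "Will adjudicate AEs and SAEs with" a second named person (Section 2.3.1.2), so it would be wrong to infer a single adjudicator. SAEs go within 48 hours to the IRB and to a safety monitor not directly related with the study (Sections 2.2.1.1.1, 2.2.3.1.1 and 2.2.3.2). A difference between arms can trigger a group review of other AEs. None of this is blinded, but it lowers the risk.
- Relatedness is not closed to controls, who have protocol acetaminophen, surface cooling and surface warming (Section 8).
- With plausible early mortality the distortion is small: one death per arm moves the difference by at most 10 points.

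A reader might infer that similar deaths will be counted differently by arm, or that the plan is tilted against hypothermia. The documents support neither: they allow differential counting and give no evidence of its occurrence or direction. A reader might also infer that deaths could be hidden. They could not: vital status, 60- and 90-day survival and ventilator-free days (zero for death before day 28) show them by arm.

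**Conclusion.** The concern holds as a defect of the SAE comparison, and only there. The SAP does not identify what is compared, the protocol's wordings give different counts for the same patients, and one of them passes deaths and organ failures through unblinded attribution. This should be fixed because safety is part of the primary outcome.

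The size cannot be taken from the documents. With 10 per arm and one early ARDS death in each, the choice of wording and the attribution move the difference by up to 10 points. With three in each, it is up to 30 points (95% CI −4 to +60), an extreme case that also needs all-or-none attribution by arm. All counts are assumptions. The textual conflict is certain; bias between arms is a possibility only.

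Aim 1 expects no significant increase in serious adverse effects. A reader might take that as the rule for declaring safety, but it is worded as an expectation. The intervals above show why non-significance in 20 patients should not be read as evidence of safety.

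**What to change.** **Protocol.** Reconcile Section 2.2.1.1.1 item 4, Section 2.2.3.2 item 2, and Section 12 (subsections 1 and 3, and Reporting requirements), so that SAE has one meaning. The rules on what goes on the AE form and what is reported quickly can stay.

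**SAP.**

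- Compare the number of patients with at least one SAE, under one seriousness definition, regardless of attribution and including all-cause deaths, over one stated window from randomisation. To the Day 7 form is one possibility, since "Patients will be seen daily by study personnel through the first 7 days for data collection" (Section 3.5).
- State how later events are shown, because the schedule in Section 6 monitors AEs to day 90.
- Take deaths from the vital-status fields, and label the count as deaths plus serious events captured on the forms. Organ failures left off the AE form under Section 12 would not be in it, and the label should make that clear.
- Show study-related events in a secondary table.
- Report counts per arm with the risk difference and 95% CI, and draw no safety conclusion from a non-significant test.

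**Optional and minor.** Extend Day 7 line 13 and its instruction in Section 10.7 from 24 h to 72 h.

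**Cost.** Wording in two documents and, if the option is taken, one form line with its instruction; no new visits. The downside is that wide intervals will make the safety statement less favourable.
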